8 DISCONTINUATION CRITERIA

8.1 Discontinuation from Study Treatment

Participants MUST discontinue investigational product (and non-investigational product at the discretion of the investigator) for any of the following reasons:

- Participant's request to stop study treatment. Participants who request to discontinue study treatment will remain in the study and must continue to be followed for protocol specified follow-up procedures. The only exception to this is when a participant specifically withdraws consent for any further contact with him/her or persons previously authorized by participant to provide this information
- Any clinical adverse event (AE), laboratory abnormality or intercurrent illness which, in the opinion of the investigator, indicates that continued participation in the study is not in the best interest of the participant
- Termination of the study by Bristol-Myers Squibb (BMS)
- Loss of ability to freely provide consent through imprisonment or involuntary incarceration for treatment of either a psychiatric or physical (eg, infectious disease) illness. (Note: Under specific circumstances and only in countries where local regulations permit, a participant who has been imprisoned may be permitted to continue as a participant. Strict conditions apply and BMS approval is required.)
- Asthma or COPD that requires systemic glucocorticoid or biologic treatment, or inhaled budesonide or equivalent at >1200 µg/day or fluticasone propionate at > 880 µg/day along with another anti-asthma/COPD drug such as a long-acting beta-agonist.
- Systemic or photo-based rescue therapy for AD ([Section 7.7.2](#)),
- Replication-competent (live) vaccine
- Grade 4 lymphopenia (ALC < 200) with repeat testing within 7 days (according to the Common Toxicity Criteria for Adverse Events [CTCAE] version 5.0)
- Elevation of ALT or AST > 5x ULN or concurrent elevations of ALT or AST > 3x ULN and bilirubin > 2x ULN
- Decline in PFT values (FEV1 and/or FVC) below 30% of the baseline values
- Diagnosis of macular edema, retinal or choroidal disease or syndrome
- Grade 2 or higher cardiac or bone marrow adverse events (with exception of ALC) according to the CTCAE version 5.0.
- Grade 3 for other system adverse events (according to the CTCAE version 5.0)
- Missed dose of ≥ 3 consecutive days or overall compliance < 85% over a period of > 30 days starting from study Day 1.

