9.2.6 Laboratory Test Result Abnormalities

The following laboratory test result abnormalities should be captured on the nonserious AE CRF page or SAE Report Form electronic, as appropriate. Paper forms are only intended as a back-up option when the electronic system is not functioning.

- Any laboratory test result that is clinically significant or meets the definition of an SAE
- Any laboratory test result abnormality that required the participant to have study treatment discontinued or interrupted
- Any laboratory test result abnormality that required the participant to receive specific corrective therapy

It is expected that wherever possible, the clinical rather than laboratory term would be used by the reporting investigator (eg, anemia versus low hemoglobin value).

Clinically significant changes, in the judgment of the investigator, in laboratory parameters (abnormalities) will be recorded as AEs. During the treatment period, all total WBC and WBC differential results will be blinded. Reductions in ALC levels is a known PD effect of BMS-986166. If any of the following results are observed, the investigator will be notified and asked to repeat the laboratory tests within approximately 7 days:

- Absolute lymphocyte count [ALC] < 200 cells/ μ L
- Absolute neutrophil count [ANC] < 1000 cells/ μ L
- Total WBC > 20,000 cells/ μ L

If the repeat values also exceed these limits, the investigator will be informed that the patient's results for the abnormal parameter have fallen below the acceptable threshold.

If ANC or total WBC counts are confirmed below the acceptable limits, the Medical Monitor will contact the treating investigator to request close monitoring for risk of serious infection and appropriate follow-up, at the discretion of the investigator.

If the ALC is confirmed < 200 cells/ μ L, the investigator will discontinue investigational drug and then consult with the Medical Monitor. Laboratory testing will be repeated weekly until ALC is > 500 cells/ μ L.

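### The only on-treatment total WBC alert is an upper limit, but the follow-up wording is for low counts, so a confirmed high WBC does not trigger the infection-monitoring request as written

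*Combined protocol and SAP*

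**What the plan says.** Section 9.2.6 states that during the treatment period "all total WBC and WBC differential results will be blinded". The site therefore learns of an abnormal count through the alerts. Three are listed, in cells/µL: ALC < 200, ANC < 1000, and "Total WBC > 20,000 cells". For any of them, "the investigator will be notified and asked to repeat the laboratory tests within approximately 7 days".

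Three sentences say what follows a confirmed result:

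1. For all parameters: "If the repeat values also exceed these limits", the investigator is told that the "results for the abnormal parameter have fallen below the acceptable threshold".
2. For ANC and total WBC: "If ANC or total WBC counts are confirmed below the acceptable limits", the Medical Monitor contacts the investigator to "request close monitoring for risk of serious infection and appropriate follow-up, at the discretion of the investigator".
3. For ALC: a confirmed value under 200 stops study drug, with weekly testing until the count is above 500.

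The only other numerical WBC limits are in Section 6.2, which excludes a count below 3000/µL or above 14,000/µL at Screening or Baseline. Those are entry criteria and do not apply on treatment.

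**The concern.** Two of the alerts are lower limits and the third, total WBC, is an upper limit. Both follow-up sentences that cover WBC are worded as if it were a lower limit. Followed as written, a participant with a confirmed WBC above 20,000 generates a notice giving the wrong direction, and the infection-monitoring contact is not made.

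That contact is a safety step in a trial of two drugs whose mechanism Sections 3.3.1 and 3.3.2 describe as immunosuppression, with infections named among the events of interest in Section 9.2.8. Sentence 2 names total WBC in a rule about serious infection, so the protocol evidently means some WBC result to lead there. A notice saying that a count has fallen is also easy to accept at face value in this trial, because lowered lymphocytes are an expected effect of BMS-986166.

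**Working it through.** No arithmetic is involved. The check compares the direction of each alert with the direction of the sentences that act on it.

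| Parameter | Listed alert (cells/µL) | Direction | Sentence 1: trigger | Sentence 1: message | Further action |
|---|---|---|---|---|---|
| ALC | < 200 | low | met | correct | Sentence 3, triggered by < 200: consistent |
| ANC | < 1000 | low | met | correct | Sentence 2, triggered by a low count: consistent |
| Total WBC | > 20,000 | high | met | wrong direction | Sentence 2, triggered by a low count: not met |

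**Sentence 1.** Its trigger refers to exceeding the listed limits, which covers all three alerts. A confirmed WBC of, say, 22,000 (an illustrative value) therefore produces a second notice, but the notice says that the result has fallen below the threshold.

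**Sentence 2.** The same value of 22,000 is above 20,000, so the condition of being confirmed below the limit is false and the contact is not triggered. A low WBC cannot trigger it either, because there is no listed lower limit against which to confirm it. Listed limits able to trigger sentence 2: ANC one, total WBC none.

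**Is the WBC sign simply misprinted?** A lower limit of 20,000 is not plausible. Section 6.2 excludes anyone above 14,000 at entry, so every eligible participant would start below it.

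**Is there a lower on-treatment WBC limit elsewhere?** The Synopsis, Section 5.1 and Section 9.4.9 say only that counts are monitored centrally and withheld from sites. Section 6.2 applies at entry. Section 8.1 stops drug for Grade 2 or higher bone marrow adverse events (ALC excepted), but that is an adverse-event grading rule. It is neither a total WBC alert nor a route to the infection-monitoring request. None of these supplies the missing limit.

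**Which word is wrong?** Two repairs fit the text. Either the sentences should refer to results outside the limits, or a lower WBC limit was left out. The first is more likely, since the limits referred to can only be those just listed. The second cannot be excluded: the entry criteria use both a lower and an upper WBC limit, and Section 5.1.2 justifies the visit schedule partly by the need to detect very low leukocyte counts.

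**The case against.** The strongest reply is that the intent is plain. The limits in sentence 2 can only be those listed just above it, and the only WBC limit there is 20,000, so naming total WBC makes sense only if a high count is meant. On that reading nothing is missing. On a strictly literal reading, the sentence treats low counts as the infection signal, and nothing else in the protocol says that a high WBC should prompt the request. A Medical Monitor told of a confirmed WBC above 20,000 would hardly do nothing.

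The affected step is also a request, with follow-up left to the investigator, and not a stopping rule. By then the investigator has had the first alert, repeated the test and been notified again, and can infer the direction because there is only one WBC alert. Other provisions help:

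- Section 8.1 requires stopping drug for "Any clinical adverse event (AE), laboratory abnormality or intercurrent illness which, in the opinion of the investigator", makes continuing unsuitable.
- Section 9 requires immediate safety concerns to be discussed with the sponsor.
- Temperature is taken at every treatment visit (Table 2-2).
- Unscheduled visits provide for hematology and a targeted examination (Table 2-3).
- Counts are monitored centrally (Sections 5.1 and 9.4.9), and a DMC reviews safety (Section 5.1.4).

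Much of this stands, and it keeps the weight low. It is also fair to call this one wording slip appearing in two sentences, and not a deliberate design choice. But neither reading rescues the text. Taken literally, the WBC part of the rule does nothing; taken by intent, the reader must override the word in the rule. Only the follow-up is discretionary; the Medical Monitor's contact is stated as something that will happen. The general provisions depend on individual judgement or on other routine checks, and none restores the specific trigger.

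**Conclusion.** The point holds. Section 9.2.6 contradicts itself on total WBC: the one listed limit is an upper one, the confirmation notice describes it in the wrong direction, and the infection-monitoring request cannot be triggered by it as written.

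The size is modest: one of three alerts, one trigger that cannot be met and one message that is wrong, confined to a confirmed WBC above 20,000. ALC and ANC handling is consistent. How many participants would be affected cannot be derived from the documents. There is no effect on endpoints, analyses or sample size.

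The conclusion rests on reading the current text as it stands, and on the absence of any other on-treatment total WBC limit in the protocol. The central laboratory's alert specification is not part of the documents and may already be correct. This should be corrected at the next amendment, because it is an operative safety rule for blinded sites and the correction is nearly free.

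**What to change.** 1. The sponsor confirms that the upper limit of 20,000 cells/µL is what was intended. A lower WBC limit should be added only if one was meant.
2. In the confirmation notice, say that the result is outside its acceptable limit, and give the direction for each parameter: ALC low, ANC low, total WBC high.
3. In the Medical Monitor sentence, replace the general condition with explicit ones: ANC confirmed < 1000 cells/µL, or total WBC confirmed > 20,000 cells/µL.
4. Check that the central laboratory's alert text matches.

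The cost is two reworded sentences, one sponsor confirmation and one check of the alert text. Visits, sample size and analyses do not change.

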9.2.7 Potential Drug Induced Liver Injury (DILI)

Wherever possible, timely confirmation of initial liver-related laboratory abnormalities should occur prior to the reporting of a potential DILI event. All occurrences of potential DILIs, meeting the defined criteria, must be reported as SAEs (see [Section 9](#) and [Appendix 3](#) for reporting details).

Potential drug induced liver injury is defined as:

- AT (ALT or AST) elevation > 3 times upper limit of normal (ULN) AND
- Total bilirubin > 2 times ULN, without initial findings of cholestasis (elevated serum alkaline phosphatase) AND
- No other immediately apparent possible causes of AT elevation and hyperbilirubinemia, including, but not limited to, viral hepatitis, pre-existing chronic or acute liver disease, or the administration of other drug(s) known to be hepatotoxic.

9.2.8 Monitoring of Participants with Adverse Events of Interest (AEIs)

Adverse events of interest (AEIs) are AEs for a particular product or class of products that a Sponsor may wish to monitor carefully. AEIs may be serious or nonserious. Such events may require further investigation to better characterize and understand them in addition to the conventional safety monitoring employed in the study. In the branebrutinib clinical development program, infection AEs have been identified as potential AEIs; however, there has been no definitive assessment on the causal relationship between these events and treatment with branebrutinib. Therefore, additional information about infection AEs may be collected on the eCRF in order to better characterize and understand them.

Potential AEs of interest that may be a consequence of S1PR1 modulation will therefore be monitored in the IM018005 study. These AEs include:

- **Bradycardia and heart conduction abnormalities:**

Dose-related transient, reversible bradycardia and first-degree atrioventricular block were reported primarily as first dose effects in fingolimod studies. The HR reduction observed with S1PR1 agonists is an expected effect of S1PR modulation and appears to be conducted through the same pathway as vagus nerve stimulation. In addition, these negative chronotropic effects of S1PR1 agonists appear to attenuate over time secondary to S1PR desensitization and internalization on cardiac myocytes.¹¹⁹ Because of its biased ligand properties, both nonclinical and clinical data suggest that this effect is less with BMS-986166 (Section 3.2 and IB).

Nevertheless, ECG assessment predose and at 1, 2, 4, and 6 hours post-dose will be obtained; in addition to hourly monitoring of the HR and blood pressure on Day 1. Standard 12-lead ECG will be collected and reviewed with every subsequent visit.

Clinicians should be particularly mindful of participants who have a low HR at baseline (spontaneously or through drug-induced β -receptor blockade), prior to administration of the investigational drug. Atropine IV is recommended as the first-line treatment of bradycardia, up to a maximum daily dose of 3 mg. Furthermore, the common guidelines for treatment of bradycardia (eg, Advanced Cardiac Life Support [ACLS] guidelines) should be followed as appropriate.

- **Pulmonary effects:**

An initial sharp decrease followed by a slow progressive decline over time in FEV1 was observed in fingolimod clinical studies. Nonclinical toxicity studies however with BMS-986166 have not revealed the potential for pulmonary toxicity at doses considerably higher than the pharmacologically active dose. PFTs including FEV1, FVC, and diffusion capacity of carbon monoxide (DLCO), will be measured in all participants. Every participant whose PFTs are abnormal will be followed until such time as resolution is confirmed or no further improvement is expected by the investigator.

Any condition that might affect the outcome of pulmonary function testing including infection, respiratory symptoms, occupational exposures (including asbestos) and cigarette smoking needs to be collected before PFT testing and transcribed to the PFTs eCRF page. If participants experience a decline in PFT values (FEV1 and/or FVC) below 30% of the baseline values, treatment should be discontinued.

If a participant discontinues due to a respiratory AE, the investigator should ensure that the patient has adequate evaluations as clinically indicated by a pulmonologist for the AE. Further evaluations will be conducted until such time as resolution is confirmed or no further improvement is expected by the investigator (based on a follow-up period of not less than 3 months).

- **Hepatotoxicity:**

Fingolimod caused frequent, reversible liver enzyme elevations greater than 3-fold above the ULN in up to 12% of patients; this was a significant cause of cessation of therapy. In this study, clinical blood chemistry analyses to assess liver function tests (LFTs) will be performed. Every patient whose LFTs are abnormal will be followed until values return to baseline.

Refer to [Section 9.2.6](#) and [Section 9.2.7](#) for instructions regarding hepatotoxicity.

- **Macular edema:**

Instances of serious macular edema were reported in fingolimod renal transplant studies, and a 0.8% incidence was reported as an SAE in fingolimod (1.25 mg dose) MS clinical studies. Nonclinical studies with BMS-986166 have not revealed eye-related toxicities. In this study, visual acuity (VA) testing and OCT will be performed in all participants at screening and the end of study visits or early termination. In addition, participants will be questioned about visual signs or symptoms at each study visit and instructed to inform the investigator if they develop symptoms between visits. For participants with visual symptoms suggestive of macular edema, OCT and ophthalmologic examination, including visual acuity testing and dilated ophthalmoscopy, will also be performed. Every participant whose ophthalmic evaluations reveal abnormalities will be followed until values return to baseline.

Study drug must be discontinued in any participant who has a diagnosis of macular edema. Participants with a diagnosis of macular edema must be followed up monthly or more frequently if needed based on the ophthalmologist's judgment. Further ophthalmological evaluations will be conducted until such time as resolution is confirmed or no further improvement is expected by the ophthalmologist (based on a follow-up period of not less than 3 months). If the participant does not show definite signs of improvement on examination 6 to 8 weeks after discontinuation of investigational drug, then therapy for macular edema in conjunction with an ophthalmologist experienced in the management of this condition should be initiated.

- **Opportunistic or serious infections:**

TB, serious bacterial infections, systemic fungal infections, viral infections such as herpes infections (including herpes zoster and disseminated herpes simplex), and protozoal infections should be reported as AEs and treated accordingly.

Malignancies

Malignancies such as melanoma, basal cell carcinoma, breast cancer, lymphoma (cutaneous T-cell lymphoproliferative disorders or diffuse B-cell lymphoma), and seminoma have also been reported for the class of S1P receptor modulators. Malignancy should be reported as AEs and referred accordingly to the appropriate specialist.

Progressive multifocal leukoencephalopathy (PML)

PML is an opportunistic viral infection of the brain caused by the John Cunningham virus (JCV) that typically occurs in patients who are immunocompromised and may lead to death or

severe disability. JCV infection resulting in PML has been observed in patients treated with immunomodulatory therapies for MS and has been associated with some risk factors (eg, polytherapy with immunosuppressants, severely immunocompromised patients). Typical symptoms associated with PML vary, progress over days to weeks, and include progressive weakness on 1 side of the body or clumsiness of limbs, disturbance of vision, and changes in thinking, memory, and orientation leading to confusion and personality changes.

Investigators should be vigilant for clinical symptoms or other findings that may be suggestive of PML. If PML is suspected, a neurologist consultation should be obtained and magnetic resonance imaging (MRI) should be requested and treatment should be discontinued.

Posterior reversible encephalopathy syndrome (PRES)

PRES is a syndrome characterized by sudden onset of severe headache, confusion, seizures, and visual loss. If a participant develops any unexpected neurological or psychiatric symptoms/signs (eg, cognitive deficits, behavioral changes, cortical visual disturbances, or any other neurological cortical symptoms/signs), any symptom/sign suggestive of an increase of intracranial pressure, or accelerated neurological deterioration, the physician should promptly schedule a complete physical and neurological examination and should consider an MRI. If PRES is suspected, treatment should be discontinued.

9.2.9 Other Safety Considerations

Any significant worsening noted during interim or final physical examinations, electrocardiogram, x-ray filming, any other potential safety assessment required or not required by protocol should also be recorded as a nonserious or serious AE, as appropriate, and reported accordingly.

9.3 Overdose

For this study, any dose of BMS-986166 or branebrutinib greater than 2 daily doses of study treatment within a 24-hour time period will be considered an overdose. See [Section 9](#) for AE assessment and reporting procedures regarding suspected overdose and intentional overdose.

Based on the IB, there has been no clinical experience nor known specific antidote for overdose with either BMS-986166 or branebrutinib.^{38,47}

In the event of an overdose, the investigator should:

- 1) Contact the Medical Monitor immediately.
- 2) Closely monitor the participant for AEs/SAEs and laboratory abnormalities.
- 3) Obtain a plasma sample for PK analysis within 4 hours of the overdose if requested by the Medical Monitor (determined on a case-by-case basis).
- 4) Document the quantity of the excess dose as well as the duration of the overdosing in the eCRF.

Decisions regarding dose interruptions or modifications will be made by the investigator in consultation with the Medical Monitor based on the clinical evaluation of the participant.

9.4 Safety

An external, independent DMC will be empaneled to review safety on a prescheduled and ad-hoc basis, in addition to contemporaneous safety monitoring by the study team. Planned time points for all safety assessments are listed in the Schedule of Activities ([Section 2](#)).

9.4.1 Physical Examinations

A complete physical examination will include general appearance, vital signs, eyes, ears, nose, mouth, throat, neck, respiratory, cardiovascular, respiratory, gastrointestinal/abdomen, lymphatic, musculoskeletal, skin, psychiatric, and neurologic examinations.

A targeted physical examination will include any organ system associated with an AE, or a laboratory abnormality. Refer to the Schedule of Activities ([Section 2](#)). The examination includes examination of the abdomen, conjunctival mucosae, heart, lungs, lymph nodes, oral mucosa, skin, and any sites deemed necessary by the investigators based on symptoms or other findings.

9.4.2 Vital signs

Refer to the Schedule of Activities ([Section 2](#)).

